3.4.2.3 Exploratory Efficacy Variables

Plasma EBV DNA levels were monitored for 12 months by qPCR.

3.4.3 Pharmacokinetics

Pharmacokinetic endpoints include observed plasma concentrations and estimated PK parameters for nanotinostat and ganciclovir. For details of PK parameters, please refer Section 4.7.3.

3.5 Data Quality Assurance

Report summaries will be generated using validated Base SAS® software, version 9.4 or higher, on a PC or server-based platform. Additional validated software may be used to generate analyses, as needed.

All SAS programs that create outputs or supporting analysis datasets will be validated by a second statistical programmer or biostatistician. At a minimum, validation of programs will consist of a review of the program log, review of output or dataset format and structure, and independent confirmatory programming to verify output results or dataset content. Additionally, all outputs will undergo a review by a senior level team member before finalization.

The content of the source data will be reviewed on an ongoing basis by project statistical programmers and statisticians. Data will be checked for missing values, invalid records, and extreme outliers through defensive programming applications, analysis-based edit checks, and other programmatic testing procedures. All findings will be forwarded to the project data manager for appropriate action and resolution.

4. STATISTICAL METHODS

4.1 General Methodology

Data will be analyzed by Emanate biostatistics personnel. Statistical analyses will be reported with tables, figures, and listings, presented in rich text format, and using recommended ICH numbering. Output specifications for all tables, figures, and listings will be in conformance with guidelines specified by the ICH in Appendix 7 of the Electronic Common Technical Document Specification (Apr 2003).

4.1.1 Reporting Conventions

Tables and figures will be summarized by cohort and study phase. Tables will also include a column for all patients who receive the capsule formulation. In general, all data collected, and any derived data will be presented in patient data listings, for all enrolled patients. Listings will be ordered by site, study phase, patient number, cohort,

and assessment or event date. The cohort presented in listings will be based on the planned assignment, unless otherwise noted.

Summaries will be based on patient data from both the dose escalation and dose expansion phases up until the time when the final dose escalation patient has completed at least 12 months of follow-up from their first disease response assessment after two cycles of therapy, or until all patients have discontinued the study, died, withdrawn consent, discontinued, or are lost to follow-up, whichever occurs first.

In general, continuous variables will be summarized to indicate the study population sample size (N), number of patients with available data (n), mean, SD, median, minimum, and maximum values. Categorical variables will be summarized by the population size (N), number of patients with available data (n), number of patients in each category, and the percentage of patients in each category. Unless otherwise noted, the denominator to determine the percentage of patients in each category will be based on the number of patients with available data. Select ordinal data may be summarized using both descriptive statistics and counts and percentages of patients in each category, as appropriate.

Non-zero percentages will be rounded to one decimal place. Rounding conventions for presentation of summary statistics will be based on the precision of the variable of summarization, as it is collected in its rawest form (i.e., on the electronic case report form [eCRF] or as provided within an external file) and are outlined as follows:

- The mean and median will be rounded to one more decimal place than the precision of the variable of summarization.
- Measures of variability (e.g., SD, SE) will be rounded to two more decimal places than the precision of the variable of summarization.
- Minimum and maximum values will be presented using the same precision as the variable of summarization.

Other statistics (e.g., CIs) will be presented using the same general rules outlined above or assessed for the most appropriate presentation based on the underlying data.

No formal statistical analysis will be performed to compare cohorts. This study is exploratory in nature; descriptive statistics will be tabulated by study phase and cohort and reviewed to evaluate all study endpoints.

4.1.2 *Summarization by Visit*

In general, data summarized by study visit will be based on the nominal, scheduled visit label as reported on the eCRF. Data collected for the last patient visit will be summarized separately and this summary will be labeled as “End of Treatment” in the analysis.

For laboratory data summaries, data summarized by study visit will be based on the nominal, scheduled visit label as reported on the eCRF when available. If the scheduled visit is not available, then all data collection, including unscheduled and early

termination visits, will be reassigned a study visit based on the actual days relative to baseline using the visit windows identified in [Table 3](#) below.

Table 3 Visit Windows for Analysis

Scheduled Visit	Target Study Day	Study Day Interval
Baseline	0	≤ 0
Cycle 1 Day 1	1	1
Cycle 1 Day 2*	2	2
Cycle 1 Day 8	8	3 – 11
Cycle 1 Day 15	15	12 – 18
Cycle 1 Day 22	22	19 – XX^{**}
Cycle 2 Day 1	$XX + 1$	$XX + 1$
Cycle 2 Day 8	$XX + 8$	$(XX + 2) – (XX + 11)$
<hr/>		
...		

*Note Cycle 1 is the only cycle with a schedule Day 2 visit

** Day 22 is the last scheduled visit within each cycle, and the end of the study interval (XX) is calculated as the day before the start of the subsequent cycle.

If more than one value is mapped to the same visit, the value collected closest to the target study day will be considered for summarization. If two values collected on different days are mapped to the same scheduled visit and are equidistant from the target study day, the earlier of the values will be considered. The visit displayed on subject data listings will be reflective of the scheduled visit label as reported on the eCRF. Study days relative to baseline will be displayed for each visit to indicate to which visit the assessment may have been reassigned, if any.

Otherwise, data collected at unscheduled visits will not be included in by-visit summaries but will be considered when endpoint derivations potentially include multiple visits (e.g., determination of baseline value, determination of worst post-baseline value, etc.). All data will be included in patient listings.

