12.2. Description of Statistical Methods

Analyses performed for this study will utilize descriptive statistics. For continuous variables, the following information will be presented by cohort and study phase: n, mean, standard deviation, median, minimum, and maximum. Baseline will be the last observation prior to treatment. For categorical variables counts and percentages will be used.

The clinical outcomes of primary interest are overall response rate (ORR: complete or partial response) and duration of response (DoR). Efficacy will be presented as the percentage of patients with CRs, PRs, and SD. ORR will be calculated as CR + PR; disease control rate will be calculated as CR + PR + SD. Response criteria will follow the recommendations of Cheson et al., 2014.²⁸ The analysis of study data will be based on patient data from both the dose escalation (Phase 1b) and dose expansion (Phase 2 and Tablet cohort) parts up to the time when: i) all Phase 1b patients have completed at least 12 months of follow-up from their first disease response assessment after 2 cycles of therapy or have discontinued from the study, and ii) all patients have been followed for DoR for a maximum period of 12 months from the first dose of study medication, have died, withdrawn consent, discontinued, or are lost to follow up, whichever occurs first. The additional data for any patients continuing to receive study drugs or remaining in safety or survival follow-up beyond the final cutoff point will be summarized in a final Clinical Study Report.

The ORR and CR rates will be summarized by cohort and study phase with exact 95% confidence Intervals (CIs).

Duration of response is defined as time from date of first observed complete or partial response to the date of disease progression, death due to any cause, or last adequate (radiographic) response assessment. The DoR will be estimated for the RP2D dose patients using Kaplan-Meier estimates where patients still on treatment after 12 months will be censored.

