1. INTRODUCTION

The purpose of this Statistical Analysis Plan (SAP) is to provide comprehensive and detailed descriptions of the methods and presentation of data analyses proposed for Viracta Therapeutics, Inc. Protocol VT3996-201 (A Phase 1b/2 Open-Label, Dose Escalation and Expansion Study of Orally Administered VRx-3996 and Valanciclovir in Subjects with Epstein-Barr Virus-Associated Lymphoid Malignancies). Descriptions of planned analyses for the clinical study report (CSR) are provided in order to avoid post hoc decisions that may affect the interpretation of the statistical analysis. Both the statistical methods applied to the study design and the planned analyses for this study are consistent with the International Council for Harmonisation (ICH) guideline *Statistical Principles for Clinical Trials (E9)* (1998). The final study analysis will be performed when the last patient with a partial response (PR) or complete response (CR) is followed for 12 months, and all enrolled subjects have completed efficacy, safety and other assessments.

This SAP will be finalized prior to data analysis and before database lock to provide comprehensive details of the tables, figures, and listings to be presented in the CSR. Any changes between the statistical methods provided in the clinical study protocol and this SAP will be explained herein; any changes or deviations from this SAP relative to the final analysis will be fully documented in the CSR. Minor changes or deviations from the templates for tables, figures, and listings need not be documented in the CSR.

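### SAP 4.1.1 lets one Phase 1b patient set the data cutoff for all summaries and drops Protocol 12.2's 12-month follow-up condition for all patients, without listing the change

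*SAP*

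**What the plan says.** **Protocol 12.2** sets one cutoff for the "dose escalation (Phase 1b) and dose expansion (Phase 2 and Tablet cohort) parts up to the time when" two conditions are both met. Condition (i) asks that all Phase 1b patients have at least 12 months from their first response assessment. The text then continues: "or have discontinued from the study, and ii) all patients have been followed for DoR for a maximum period of 12 months" from first dose, or have died, withdrawn, discontinued or been lost. Data arising after the cutoff go into a final study report. The same section states: "The clinical outcomes of primary interest are overall response rate (ORR: complete or partial response) and duration of response (DoR"). It also says which patients DoR is estimated in: "The DoR will be estimated for the RP2D dose patients using Kaplan-Meier estimates where patients still on treatment after 12 months will be censored".

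**SAP 4.1.1** draws its summaries from dose escalation and dose expansion together, "up until the time when the final dose escalation patient has completed at least 12 months of follow-up from their first disease response assessment". That assessment is the one made once two cycles have been given. The alternative limb reads: "or until all patients have discontinued the study, died, withdrawn consent, discontinued, or are lost to follow-up, whichever occurs first".

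**SAP Section 1** says the final analysis "will be performed when the last patient with a partial response (PR) or complete response (CR) is followed for 12 months", and that by then "all enrolled subjects have completed efficacy, safety and other assessments". It gives no start point for the 12 months. It also undertakes to explain in the SAP any change from the protocol's statistical methods.

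**SAP 4.6.5.2** refers to a data analysis cutoff date when describing who is censored for PFS and DoR, but does not define that date.

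**SAP 4.9** lists changes to Cohort 1 and Cohort 3 dosing, central scan review and urine PK. It lists nothing on the cutoff.

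**The concern.** Condition (ii) in Protocol 12.2 is the only follow-up requirement that reaches Phase 2 and tablet patients, and SAP 4.1.1 leaves it out. These patients come last. Phase 2 uses the RP2D set when Phase 1b concludes (Protocol 3.2.2), and the tablet cohort opens once Phase 2 has filled (Protocol 3.3). A cutoff timed on a Phase 1b patient therefore falls hardest on the patients who make up most of the RP2D group, in whom DoR is to be estimated.

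The SAP also loses the exception for Phase 1b patients who have discontinued. The list of exits, which excuses individual patients in the protocol, becomes an alternative trigger that needs all patients to have left. The cutoff could therefore come early or have no foreseeable date, depending on what one patient does. Section 1 adds a third rule. The responder follow-up that it waits for could lie beyond the point at which 4.1.1 stops taking data into the tables.

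**Working it through.** **1. The two rules side by side**

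| Element | Protocol 12.2 | SAP 4.1.1 |
|---|---|---|
| Phase 1b follow-up | All Phase 1b patients, at least 12 months from first response assessment | The final Phase 1b patient, same 12 months |
| Exception for discontinued Phase 1b patients | Yes | No |
| 12-month DoR condition for all patients | Yes, joined by *and* | Absent |
| Role of the exit list | Excuses each patient who leaves | Alternative trigger, once all have left; earlier limb governs |
| Later data | Final study report | No matching provision |

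I read the protocol's maximum of 12 months as a cap: the condition is met once each patient has reached 12 months from first dose or has left.

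**2. Earliest SAP 4.1.1 cutoff**

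Inputs: cycle of 28 days (Protocol 3); first disease assessment after Cycle 2 (Protocol 7); year = 365.25 days and month = 30.44 days (SAP 4.1.5). Day 0 is the last Phase 1b patient's first dose.

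- First assessment: 2 × 28 = 56 days.
- Cutoff: 56 + 365.25 = 421.25 days; 421.25 / 30.44 = 13.8 months.

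This is the earliest date, since the SAP says at least 12 months. Day 56 is nominal: the visit window is ±3 days, and assessment timing may be adjusted.

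**3. Follow-up left for later patients**

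A patient starting *g* days after day 0 has 421.25 − *g* days from first dose. Reaching 12 months needs 421.25 − *g* ≥ 365.25, so *g* ≤ 56.

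| Start *g* (days) | From first dose (days) | Months | Short of 12 months by (days) |
|---|---|---|---|
| 28 | 393.25 | 12.9 | none |
| 90 | 331.25 | 10.9 | 34 |
| 180 | 241.25 | 7.9 | 124 |
| 365.25 | 56 | 1.8 | 309.25 |

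A start after about day 365 puts the first scheduled post-baseline scan beyond the cutoff. None of this needs an accrual rate.

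**4. Patient counts, illustration only**

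The documents give no accrual rate. Assume even accrual, with Phase 2 opening at day 28, when the last Phase 1b patient's DLT period ends.

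- 1 per month: 1 of 30 Phase 2 patients can have 12 months; 17 of 30, and all 10 tablet patients, are not yet dosed at the cutoff.
- 4 per month: all 40 are dosed; 4 of 30 and 0 of 10 can have 12 months.
- 15 per month: 14 of 30 and 0 of 10 can have 12 months.

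If Phase 2 opens after day 56, no Phase 2 or tablet patient can, at any rate.

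**5. If the last Phase 1b patient leaves early**

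If that patient leaves before 12 months, or never has the post-Cycle 2 assessment, the first limb is never met. Only the second remains. Survival contacts run at least every 3 months with no scheduled end (Protocol 6.3.3; removal criteria in 3.17). The cutoff then waits for all of the planned 25 + 30 + 10 = 65 patients to be off study.

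**The case against.** The best defence is that SAP 4.1.1 is a shortened copy of Protocol 12.2 and will be applied as the protocol intends. The final dose escalation patient having completed may simply mean that all have. At least 12 months is a minimum, so a later cutoff is allowed. The second limb lists discontinuing the study and, separately, discontinuing; the second may mean stopping treatment, in which case open-ended survival follow-up would not hold the cutoff. DoR is a secondary objective in both documents, the analyses are descriptive with no hypothesis test, and listings carry all collected data.

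These points limit the harm. None of them restores condition (ii) or supplies a single date.

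Several stronger readings are tempting but not supported:

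- *Sections 1 and 4.1.1 flatly contradict each other.* One says when the analysis is run, the other which data enter summaries. Both can be followed literally. The trouble is the effect: follow-up that was waited for may be left out.
- *PFS and DoR are censored at the undefined cutoff.* The cutoff decides which data enter. SAP Table 4 sets the censoring date for patients alive without progression as the last disease assessment.
- *The SAP denies later patients 12 months from response that the protocol guaranteed.* Protocol 12.2 counts from first dose. Its own floor for a week-8 responder who stays on study is 365.25 − 56 = 309.25 days, or 10.2 months from response.
- *The tablet cohort is excluded.* SAP 4.1.1 does not name it, but Protocol 12.2 counts it within dose expansion, and the SAP's extra column for capsule patients implies that tablet patients are tabulated.

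**Conclusion.** The point holds as an undocumented departure from Protocol 12.2 that, followed as written, can give a worse result. The cutoff can fall as early as 13.8 months after the last Phase 1b patient's first dose. Only later patients dosed within 56 days of that dose are then assured room for the protocol's 12 months. The shortfall is *g* − 56 days for a patient starting *g* days later: 34 days at day 90 and 124 at day 180. The consequence is immature DoR and PFS summaries for Phase 2 and tablet patients. Data are not lost, because listings show everything and the protocol sends later data to a final report.

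The text comparison is firm. The size rests on a literal reading, a first assessment at day 56 and the minimum 12 months; patient counts also need an assumed accrual rate. A reader might want the chance that the last Phase 1b patient leaves early. The documents give no basis for one, so both outcomes stand as possibilities without probabilities.

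**What to change.** - **SAP 4.1.1:** replace the sentence with Protocol 12.2's two conditions joined by *and*, covering Phase 1b, Phase 2 and the tablet cohort. Keep the exception for Phase 1b patients who have discontinued, and apply the exit list patient by patient. Do not add progression as an exit: Protocol 12.2 does not list it, and it could shorten overall survival follow-up.
- **SAP Section 1:** align with the same cutoff, and give the start point for the 12 months of responder follow-up.
- **SAP 4.6.5.2:** name this date as the data analysis cutoff date. Table 4's censoring dates need no change for this purpose.
- **SAP 4.9:** if a different cutoff is intended, list it and explain it.

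The edits are wording only. The cost in time is that the analysis may wait up to 12 months from the last patient's first dose. If that patient starts *s* days (more than 56) after the last Phase 1b first dose and stays on study, this is *s* − 56 days later than the earliest SAP 4.1.1 date. Under the illustrative accrual of 15, 4 or 1 patients per month, the cutoff would be about 15.5, 22.7 or 51.9 months after that dose, instead of 13.8. Protocol 12.2 already requires this wait.

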4.1.3 Data Handling Rules

Unless otherwise noted, values reported as greater than or less than some quantifiable limit (e.g., “ < 1.0 ”) will be summarized with the sign suppressed in summary tables and figures, using the numeric value reported. Data will display on patient listings to include the sign.

4.1.4 Baseline Value

Unless otherwise noted, the baseline value will be defined as the last value reported prior to first dose of study drug.

4.1.5 Standard Calculations

Where appropriate, the calculated study day of each assessment or event will be presented with the assessment or event date on patient data listings, where study day will be determined as:

- The assessment/event date minus the date of first dose of study drug, if the assessment/event date is prior to the date of first dose; and
- The assessment/event date minus the date of first dose of study drug, plus one, if the assessment/event date is on or after the date of first dose.

Other variables requiring calculations will be derived using the following formulas:

- **Days:** A duration between two dates expressed in days will be calculated using the following conventions:
 - Later date – earlier date + 1, if the earlier date is on or after the date of first dose of study drug; or
 - Later date – earlier date, if the earlier date is prior to the date of first dose of study drug.
- **Months:** A duration expressed in months will be calculated by dividing the duration in days by 30.44.
- **Years:** A duration expressed in years will be calculated by dividing the duration in days by 365.25.
- **Change from Baseline:** Change from baseline will be calculated as the post baseline value minus the baseline value.
- **Percentage Change from Baseline:** Percentage change from baseline will be calculated as the change from baseline divided by the baseline value, multiplied by 100.

4.2 Analysis Sets

The analysis sets are defined as follows:

- Intent-to-Treat (ITT) Set: The ITT includes all enrolled patients.
- Safety Analysis Set: includes all enrolled patients who receive at least one dose of nanatinostat.
- Efficacy Evaluable Set: includes all patients with measurable/evaluable disease at screening who have met all eligibility criteria and have at least one evaluable post-baseline efficacy tumor assessment.
- Pharmacokinetic Analysis Set: includes all patients in the ITT who have received at least one post-dose PK sample obtained and analyzed (i.e. valid result being

available). The PK Analysis Set is used for tabulation of nanatinostat and ganciclovir concentrations from PK plasma samples.

4.3 Study Patients

4.3.1 Disposition of Patients

Patient disposition will be summarized for the ITT by study phase and cohort and over all patients combined. Summaries will include the number and percentage of patients in each analysis set, completing treatment, completing the study, and discontinuing treatment or study early by the primary reason for discontinuation, and status at last contact.

4.3.2 Protocol Deviations

Deviations from the protocol and relevant details will be tracked throughout the study. All protocol deviations will be listed by subject.

4.4 Demographic and Baseline Characteristics

Demographic variables including country of participation, age (<65, \geq 65, \geq 75), sex, ethnicity, and race will be summarized by study phase and cohort and over all patients combined for the intent-to-treat set. Age as collected on the eCRF will be summarized using descriptive statistics. County of participation, sex, ethnicity, race, and disease stage will also be summarized with the number and percentage of patients in each parameter category.

Medical history verbatim terms on case report forms will be mapped and tabulated to/by system organ class and preferred term using the Medical Dictionary for Regulatory Activities (MedDRA, version 25.0). Frequency counts and percentages to summarize patients reporting abnormal medical history by system organ class and preferred term will be presented. Lymphoma and non-lymphoma medical history will be summarized separately. For lymphoma medical history, the number of patients diagnosed with lymphoma in their lifetime, number refractory to last therapy received prior to entering study, and the number of patients who exhausted all prior therapies will also be summarized with the number and percentage of patients in each category. Listing will include start and stop dates or notation of ongoing for conditions continuing into treatment.

